11.12 Documentation

[Type here]

All adverse events must be documented in detail within the medical record. The patient will be observed and monitored carefully until the condition resolves, stabilizes, or its cause is identified. All adverse events, including laboratory abnormalities, will be followed up according to good medical practices. Information to be recorded includes the following:

1. Specific type of reaction.
2. Duration of reaction.
3. Severity/grade of reaction according to the NCI Common Terminology Criteria for Adverse Events 5.0 (CTCAE).
4. Suspected cause of the reaction (i.e. possibly or probably related to one of the following: study treatment, progression of disease, concurrent medications, concurrent illness, or other factors).
5. Changes made in the administration of the study drugs and other actions taken to alleviate the clinical event.
6. Patient's response to medical interventions.

11.13 Reporting

According to FDA regulations (21 CFR 312.32), IND safety reports shall address "any adverse experience associated with the use of a drug that is both serious and unexpected." The IRB will be notified of any adverse event fulfilling the following criteria:

1. The adverse event is **SERIOUS** (as defined above),
OR
2. The adverse event is not serious, but is **UNEXPECTED** and its association with the study drug, device, or research-related procedure is either **DEFINITELY**, **PROBABLY**, or **POSSIBLY RELATED**, or **UNKNOWN** (as defined above).

Federal policy [45 CFR 46.116(b)(5)] also requires that investigators inform subjects of any important new information that might affect their willingness to continue participating in the research. When an adverse event necessitates changes to the consent/assent form(s) and/or protocol, or that notification is given to currently or previously enrolled subjects, an amendment request will be submitted in conjunction with the adverse event report. The IRB will make a determination whether any new findings, new knowledge, or adverse effects should be communicated to subjects.

In accordance with IRB guidelines, serious adverse events will be reported within 10 days of the investigator's or research staff members' learning of the event to The Ohio State University Institutional Review Board. OSU IRB Event Reports should be submitted through BuckIRB at: <http://orrr.osu.edu/irb/buck-IRB/>. Events resulting in temporary or permanent interruption of study activities by the investigator or sponsor to avoid potential harm to subjects should be reported within 48 hours whenever possible.

All events that may represent unanticipated problems involving risks to subjects or others will be promptly reported (as described above), regardless of whether they occur during or after the study, or involve a subject who has withdrawn from or completed study participation. If changes to the research or consent process are proposed as a result of the event or if additional information will be provided to current and/or past participants, an amendment request will also be submitted for IRB review.

Related events involving risk but not meeting the prompt reporting requirements will be

[Type here]

reported to the IRB in summary form at the time of continuing review.

12.0 STATISTICAL CONSIDERATIONS

12.1 Statistical Data Analysis and Study Design

Feasibility will be evaluated primarily with respect to device usage, and secondarily with respect to patient satisfaction. Device usage will be evaluated by the number of minutes and sessions per 24-hour day per participant. The mean patient satisfaction scores for each Likert-type question and proportion of reporting satisfaction scores at or above 7 will be estimated in the entire sample and compared between sequence groups at the 5% significance level (two-sided).

Preliminary efficacy will be evaluated with respect to the Hot Flash-Related Daily Interference Scale (HFRDIS), hot flash number and severity (as a daily hot flash score; DHFS), and patient perception of efficacy (10-point Likert scale items). HFRDIS measurements will be evaluated at the end of each week on the study, and DHFS will be used as recorded in the daily hot flash journal. Repeated measurements will be modeled as repeated outcomes in a linear mixed effects model with fixed effects for treatment, period, and treatment-by-period interaction, and random effects for subjects and for subject-by-treatment interactions to account for correlated measurements within the same subject. The period variable will be represented in the sum-to-zero coding so that the target of inference will be the fixed main effect of treatment, tested at the 5% significance level (two-sided). Thus the treatment effect will be interpreted as time-averaged and estimated using information from the mixed model. Patient perception of efficacy will be evaluated at the end of the device period and estimated in the entire sample and compared between sequence groups.

All analyses will proceed on an intent-to-treat basis. When observations of preliminary efficacy endpoints are missing, the rest of that patient's observations may still be used in the mixed effects model. To assess the potential impact of informative loss to follow-up, we will compare patients who leave the study or cease reporting endpoints to those who provide data for the full study duration. Patients will be compared on the basis of baseline variables and available longitudinal measurements. The pattern of loss to follow-up will be reported via CONSORT chart. Potential impact on estimates will be assessed via multiple imputation. For the purpose of evaluating compliance, patients who leave the study will be recorded as not wearing the device after leaving the study, ensuring that all patients are evaluable.

As an exploratory analysis, individual components of the HFRDIS will be analyzed using the same model as the total HFRDIS. As sensitivity analyses, the preliminary efficacy analyses will be repeated allowing for temporal correlation of measures, and including as covariates any baseline variables with large imbalances.

Our feasibility target is that at least 75% of all patients meet the compliance criteria described above. The minimum number of the 38 enrolled patients meeting the compliance criteria to achieve this threshold is 23 (77%), in which case the 95% Jeffreys interval lower bound is 60% (thus we can rule out population compliance rates below 60%) (Figure 3, left). We expect the population compliance rate to be at least 85%, in which case we have at least 93% probability of

[Type here]

achieving the compliance target (Figure 3, right). With a population compliance rate of 80%, we have a 76% probability of achieving the compliance target.

[figure not shown]

Figure 3: **Left:** Jeffreys intervals (95% equal tail probability credible intervals from a Beta(0.5, 0.5) prior) corresponding to various sample proportions with 30 patients. **Right:** Probability of achieving target compliance rate for various population rates.

Power to detect a treatment effect with respect to HFRDIS and DHFS measures via the mixed model depend on the size of the average treatment effect relative to the within-subject standard deviation (i.e., Cohen's d via the SD of the error term in the mixed model) and the standard deviation of the random within-subject treatment effects. Figure 4 displays study power for different combinations of these factors, estimated via simulation of 1000 datasets per scenario. For instance, if the within-subject SD and individual treatment effect SD are equal, we have 80% power to detect an average treatment effect of 0.7 (Cohen's d).

[Type here]

[figure not shown]

Figure 4: “Indiv. Trt. Eff. SD” is the standard deviation of the individual treatment effects (random slopes in mixed model) and “Within subj. SD” is the within-subject standard deviation during each period (error term in mixed model). Variability of the random intercepts has minimal effect on power.

Data from this study will be used to design future definitive intervention studies to evaluate the efficacy of this intervention in larger randomized studies.

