1.2 Secondary Objectives

- (1) To evaluate the preliminary efficacy of EMBr Wave in reducing hot flash severity and frequency in women with a history of breast cancer.
- (2) To identify in what ways EMBr Wave has the greatest potential efficacy, such as reduction in hot flash severity, frequency, duration, sense of control, or self-esteem.
- (3) To estimate effect sizes to inform power calculations for a future Phase III trial

[Type here]

[figure not shown]

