4.0 METHODOLOGY

4.1 Entry Criteria

4.1.1 Inclusion Criteria

In order to be eligible for participation in this trial, the subject must:

1. Age \geq 18 years.
2. Women with history of breast cancer, DCIS, or LCIS (currently without evidence of malignant disease)
3. Bothersome hot flashes (defined by their occurrence of \geq 28 times per week and of sufficient severity to prompt the patient to seek therapeutic intervention). Mean severity in a day should be \geq 4/10 on log scale of 0 (none at all)-10 (extremely).
4. Presence of hot flashes for $>$ 30 days prior to study entry
5. Ability to complete questionnaire(s) by themselves or with assistance.
6. Willingness to wear EMBR Wave device during the study period

[Type here]

7. Willingness to use the EMBr Wave mobile application
8. Have a working smartphone that can download the EMBr Wave mobile application (iPhone 6 or more recent generation, Android 8.0 or more recent generation)
9. ECOG Performance Status (PS) = 0, 1
10. Ability to provide informed written consent.
11. Life expectancy ≥ 6 months

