4.4 Hot Flash Assessments

This pilot trial will be conducted to get an initial reading as to the potential benefit of EMBr Wave for diminishing distress caused by hot flashes. We do not expect that this instrument will

[Type here]

actually decrease the number of hot flashes. However, it might decrease hot flash severity and decrease the interference of hot flashes on patients' lives. The main instrument to determine the amount that hot flashes are interfering with patients' lives is by using a validated instrument called the Hot Flash-Related Daily Interference Scale (HFRDIS).³

Additionally, we will follow daily hot flash numbers and severities. The hot flash number and severity will be measured by the Daily Hot Flash Score,⁴ which is a composite entity of both frequency and severity of hot flashes. The Daily Hot Flash Score is computed by the grade of severity multiplying the frequency of the same grade hot flashes according to the hot flash diary over a 24 hour period.

The OCEAN survey will also be administered to the participant to complete at baseline. This survey assesses the participant's personal connectedness that they have with their body and to the world around them. This survey gives perspective to the information obtained from the participant while they are using the EMBr Wave.

Patients will also be given instructions on how to sync their EMBr Wave with the EMBr Wave mobile application once a day, which will allow us to collect usage data from the devices. This will be used to further understand technology adoption over the 4 weeks that patients are using EMBr Wave during study participation.

We will also evaluate patient satisfaction with device use at the end of treatment using a 10-point Likert scale and through answering several Likert-type questions related to perceived device efficacy. These items will include assessment of the ways EMBr Wave had the greatest potential efficacy, such as reduction in hot flash severity, frequency, duration, sense of control, or self-esteem, as well as device usage.

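### The only controlled diary analysis planned is the composite Daily Hot Flash Score, which cannot show whether severity or frequency changed; daily count and mean severity could be added as supportive estimates

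*Combined protocol and SAP*

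**What the plan says.** Secondary objective (1), under Secondary Objectives, is to evaluate preliminary efficacy in "reducing hot flash severity and frequency in women with a history of breast cancer". Secondary objective (3) reads "To estimate effect sizes to inform power calculations for a future Phase III trial".

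Section 4.4 treats the two dimensions differently. The investigators do not expect that the device will "actually decrease the number of hot flashes. However, it might decrease hot flash severity". The same section says "Additionally, we will follow daily hot flash numbers and severities" and measures both through the Daily Hot Flash Score (DHFS), computed as the "grade of severity multiplying the frequency of the same grade hot flashes".

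Section 12.1 lists the diary efficacy endpoint as "hot flash number and severity (as a daily hot flash score; DHFS") and models it with terms for treatment, period and their interaction, plus subject and subject-by-treatment random effects. It plans an exploratory analysis of the individual HFRDIS components. It plans no analysis of the components of DHFS.

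**The concern.** An objective that names two dimensions, for which the protocol itself holds different expectations, is addressed in the diary by one number that merges them. A lower DHFS on the device would be compatible with milder flashes, fewer flashes or both.

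No other planned analysis fills the gap. HFRDIS, the main effect measure, captures interference with daily life. The perceived-efficacy items do ask about severity and frequency, but they are rated only at the end of the device period and compared between sequence groups, so they give no device versus no-device contrast.

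At stake is how well secondary objective (1) can be answered and, if DHFS is one of the effect sizes carried forward under secondary objective (3), how useful that effect size is to the designers of a later trial. The trial is unblinded, so component estimates named in advance would also be more credible than ones chosen after the data are seen. The feasibility objective and the HFRDIS analysis are not affected.

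**Working it through.** The plan gives no figure for this point to reproduce. The power statement in section 12.1 concerns HFRDIS and DHFS, and the point does not depend on it.

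**1. What the score can and cannot separate.** Let n_g be the number of flashes of grade g in a day.

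- DHFS = sum of g × n_g
- Count N = sum of n_g
- Mean severity = DHFS / N, so DHFS = N × mean severity

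One value of the product fits many pairs of factors.

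**2. Illustration at the entry minimum.** Inclusion criterion 3 requires flashes at least "28 times per week and of sufficient severity to prompt the patient to seek therapeutic intervention", which is 28 / 7 = 4 a day. It adds "Mean severity in a day should be" at least 4 on a 0-10 scale. The grade scale of DHFS is not stated, so scoring it on the entry scale is an assumption. The starting score is 4 × 4 = 16.

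| Change | Count | Mean severity | DHFS |
|---|---|---|---|
| Severity only | 4 (0%) | 3 (-25%) | 4 × 3 = 12 |
| Frequency only | 3 (-25%) | 4 (0%) | 3 × 4 = 12 |
| Mild flashes lost (2, 2, 6, 6 become 6, 6) | 2 (-50%) | 6 (+50%) | 6 + 6 = 12 |
| Opposite movements | 5 (+25%) | 3.2 (-20%) | 5 × 3.2 = 16 |

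The first three rows share a 25% fall in DHFS. The fourth shows no change although both factors moved. A different grade scale would alter the numbers but not the ambiguity.

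**3. A limit on the remedy.** Mean severity is undefined on days without a flash. Expected flash-free days in a 28-day period, for an assumed daily mean mu:

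| mu | Poisson, 28 × exp(-mu) | Negative binomial, size 2 (assumed), 28 × (2 / (2 + mu))² |
|---|---|---|
| 4 | 0.5 | 3.1 |
| 3 | 1.4 | 4.5 |
| 2 | 3.8 | 7.0 |

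If the device lowered the mean from 4 to 2, the severity summary would lose about 3.8 days against 0.5 (Poisson), or 7.0 against 3.1 (negative binomial). The loss is unequal between conditions exactly when frequency changes, so mean severity can then be biased. The third row of the first table shows a related effect: mean severity rises although no flash became worse.

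**4. Multiplicity.** If count and mean severity were tested at 5% beside HFRDIS and DHFS, the chance of at least one false positive, assuming independence, would go from 1 - 0.95² = 9.75% to 1 - 0.95⁴ = 18.5%. Supportive estimates without formal tests add no such claim.

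**The case against.** The strongest reply is that the plan made a deliberate and cited choice. Sections 4.4 and 12.1 both say that number and severity are measured through DHFS, and secondary objective (1) can be read as a joint aim. Asking which dimension benefits belongs to secondary objective (2), which has its own questionnaire items. If the number of flashes does not fall, as section 4.4 expects, a fall in DHFS must come from severity. This is also a feasibility pilot whose main effect measure is HFRDIS.

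Much of this stands, and it keeps the point small. What it leaves open is the premise itself: whether the number stays the same is an empirical question, and no controlled analysis of the count is planned to answer it. The questionnaire items cannot, because they are not collected for the no-device period.

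A reader might go further in four ways that the documents do not support:

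- **That DHFS is the wrong endpoint, or that using it is an error.** It is defined, cited and carried consistently into section 12.1.
- **That inclusion criterion 3 obliges a separate analysis because it sets separate thresholds.** It governs eligibility and does not define outcomes.
- **That the composite costs power.** The documents give no variances for count or severity, so neither the size nor the direction of any difference in power can be derived.
- **That secondary objective (3) requires diary component effect sizes.** It does not mention the diary. That it covers DHFS is an inference.

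**Conclusion.** The point holds as an optional improvement. Followed exactly, section 12.1 would give a controlled estimate for DHFS and none for daily count or severity, so it could not show which of the two dimensions named in secondary objective (1) had changed. No stated figure is wrong, and sample size and endpoint ranking are untouched.

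The illustration (one score of 12 from count changes between 0% and -50% and severity changes between -25% and +50%) shows what the score can hide and is not a forecast. It rests on the entry minimum and on the assumed 0-10 grade scale. The flash-free-day figures rest on assumed count distributions. They show that such days cannot be presumed negligible if frequency falls.

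**What to change.** First confirm, in one line of the plan, that the diary data retain counts by grade. Then keep DHFS and the current endpoint ranking, and add to section 12.1 two supportive estimates with 95% confidence intervals and no formal tests:

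1. **Daily hot flash count**, with flash-free days entered as zero, in a mixed model with the same crossover terms as the DHFS model, for example negative binomial, reported as a rate ratio.
2. **Mean severity per flash** (DHFS divided by that day's count) by condition, shown only beside count and DHFS. State with it that it is conditional on having a flash, is undefined on flash-free days and can be biased if the device changes frequency. Report the number of flash-free days by condition.

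The cost is two more analyses of the inputs that define DHFS and a few lines of text. The downside is two more exploratory results, one of which needs careful reading. The cost is also conditional. The diary form is not in the documents, 23 participants had enrolled by the January 2022 amendment, and section 4.4 allows some to stay on paper. If only a total score was stored for a participant, neither estimate can be made for her, and the report should say how many participants contribute.

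### If the device effect changes over the four weeks and late-week scores are missing, the treatment estimate leans towards the early weeks; week terms in the model would prevent this at little cost

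*Combined protocol and SAP*

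**What the plan says.** Section 12.1 specifies a "linear mixed effects model with fixed effects for treatment, period, and treatment-by-period interaction, and random effects for subjects". A further random effect covers the interaction of subject with treatment. On the target it says: "The period variable will be represented in the sum-to-zero coding so that the target of inference will be the fixed main effect of treatment". It then adds: "Thus the treatment effect will be interpreted as time-averaged and estimated using information from the mixed model".

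Period here is the two-level crossover period. The same section speaks of the device period, and the Figure 4 caption defines the error SD as the "within-subject standard deviation during each period (error term in mixed model)". On timing, "HFRDIS measurements will be evaluated at the end of each week on the study". The calendar in section 7.2 gives four weekly HFRDIS scores and 28 daily scores in each 28-day period.

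When scores are missing, "the rest of that patient's observations may still be used in the mixed effects model". Section 12.1 also plans to compare women who leave with those who complete, to assess the impact by multiple imputation (model not described), and to repeat the analysis allowing for temporal correlation.

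**The concern.** The fixed effects allow one mean per treatment and period, so the four weeks of a month are treated as interchangeable. A woman who stops reporting after week 2 contributes only early scores, and the model lets these stand for the whole month. If the device works differently in week 4 than in week 1, the estimate leans towards the weeks that were reported. This can happen even when stopping has nothing to do with outcome.

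A second, smaller route exists. If scores drift over the month in both conditions and gaps are more common in device months, the drift leaks into the treatment contrast.

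At stake is the effect size that secondary objective (3) wants for planning Phase III. A fading effect would be overstated and a growing one understated. The temporal-correlation analysis would not reveal this, because it changes the covariance and leaves the means as they are.

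**Working it through.** **The plan's own figure.** Section 12.1 states 80% power for d = 0.7 when the within-subject SD (σ) and the SD of individual treatment effects (τ) are equal. It does not state the N behind this. Take σ = τ = 1 and m = 4 scores per period.
- Random slope: SE² = (τ² + 2σ²/m)/N = 1.5/N. At N = 24, SE = 0.25 and power = Φ(0.7/0.25 − 1.96) = 80%. At N = 50 it is 98%.
- One random effect per subject-by-treatment cell: SE² = (2τ² + 2σ²/m)/N = 2.5/N. At N = 40, SE = 0.25 and power is again 80%.

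The figure is therefore attainable at the earlier planned N of 40 under one reading, and it is not in dispute here.

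**Inputs for the check.** From the documents: N = 50 (section 1.1), four HFRDIS scores per period (section 7.2), and the model in section 12.1. Assumed: subject, slope and error SDs all 1; stopping independent of outcome; 25 women per sequence; and the weekly effects below, each averaging 0.60.

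**Approximation.** Shift ≈ (share who stop) × (mean effect in the weeks seen − mean over all weeks).
- Steep fade 1.0, 0.8, 0.4, 0.2: weeks 1–2 average 0.90, and 0.90 − 0.60 = 0.30. At 10%, 20% and 30% the shift is about 0.03, 0.06 and 0.09.
- Mild fade 0.70, 0.65, 0.55, 0.50: weeks 1–2 average 0.675, a difference of 0.075. The shift is about 0.01 to 0.02.

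**Expected generalised least squares coefficient**, with known variance components, averaged over random patterns of stopping after device week 2:

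| Weekly effect | Share stopping | Planned model, device month cut short | Planned model, woman leaves the study | With week and treatment-by-week |
|---|---|---|---|---|
| Steep fade | 10% / 20% / 30% | 0.63 / 0.65 / 0.68 | 0.62 / 0.64 / 0.66 | 0.60 throughout |
| Mild fade | 10% / 20% / 30% | 0.61 / 0.61 / 0.62 | 0.61 / 0.61 / 0.62 | 0.60 throughout |
| Steep growth (0.2 to 1.0) | 10% / 20% / 30% | 0.57 / 0.55 / 0.52 | 0.58 / 0.56 / 0.54 | 0.60 throughout |
| Constant | any | 0.60 | 0.60 | 0.60 |

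With no missing scores every model returns 0.60. At 30% stopping with the device month cut short, the SE is 0.177 for the planned model and about 0.179 with the extra terms. The largest fade shift is 0.08, and 0.08/0.177 = 0.45 of an SE.

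**Which term is needed.** A second set of assumptions used N = 40, subject SD 1.5, true average 0.70, an effect growing from 0.4 to 1.0, and weeks 3–4 missing in the same share of both months.
- At 20% missing, the planned model gives 0.66 to 0.67. A week main effect alone gives 0.66.
- At 40% missing, the planned model gives 0.63. A week main effect alone gives 0.62 to 0.63.
- Week plus treatment-by-week gives 0.70 in both cases.

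**Drift.** Under the same assumptions, take a constant effect of 0.70 and a drift of 0.1 per week in both conditions. Equal gaps give 0.70. Gaps of 20% or 40% in device months only give 0.72 or 0.74, with the direction depending on the direction of the drift. Here a plain week term is enough.

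**Consequence for Phase III.** Required N scales with 1/effect². Sizing on 0.65 when the truth is 0.60 gives (0.60/0.65)² = 0.85 of the N needed. Sizing on 0.68 gives 0.78, and sizing on 0.62 gives 0.94.

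**The case against.** A reader might infer that the estimate fails to be time-averaged whenever late scores are missing. The documents do not support that. The shift needs an effect that changes by week, or drift with unequal gaps, and no section says that either occurs. Section 4.5 describes as-needed relief by a device not expected to alter the underlying condition, which offers no reason for build-up. Section 4.4 collects usage data to study adoption over the four weeks, so change over time is of interest, but nothing is said about a changing effect.

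A reader might also infer that the plan contradicts its own claim of a time-averaged effect. That does not follow either. The phrase is derived from the sum-to-zero coding of period and reads naturally as an average over the two periods, which the model delivers. Equal weighting of weeks is not promised. What remains is that the weighting of weeks is undefined.

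The plan also has safeguards. Multiple imputation would address the problem if its model allowed means by week and treatment. It is only a sensitivity assessment, however, its model is not stated, and an imputation model with the same mean structure would reproduce the shift. Section 4.4 provides reminders and end-of-intervention paper forms, and section 4.10 anticipates excellent adherence to the device. The reminders are named for HFRDIS and the satisfaction and efficacy surveys, not for the daily score. No drop-out rate is given, so heavy late loss cannot be presumed.

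Finally, efficacy is secondary and preliminary in this feasibility pilot, and the planned model is a defensible crossover analysis. That stands, and it limits the weight of the point.

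**Conclusion.** The point holds conditionally, as a modest and inexpensive refinement and not as an error in the plan. If the device effect varies over the four weeks and late scores are missing, the planned coefficient is an observation-weighted average that leans towards the early weeks. With complete data, or with a constant effect and no drift, there is no bias.

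Under the assumptions for 50 women, the shift is 0.03 to 0.08 on 0.60 for a steep fade with 10% to 30% stopping in the device month, and 0.01 to 0.02 for a mild one. A harsher assumption (N = 40, growth from 0.1 to 1.3, weeks 3–4 missing in 40% of both months) gives 0.55 against 0.70. Weekly effects, missing rates and SDs are all assumed, since the documents supply none of them. The feasibility objective is untouched. The practical relevance is to the effect size carried forward to Phase III.

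**What to change.** In section 12.1:
- Define *time-averaged* as the equal-weight mean over the four weeks and the two periods.
- Add week within period (four levels, sum-to-zero coded) and treatment-by-week to the fixed effects for HFRDIS and the daily hot flash score. The treatment main effect stays the target of inference. A week main effect alone does not remove the shift from a week-varying effect.
- State that the imputation model includes week-by-treatment means.

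The cost is SAP wording and six fixed-effect parameters (three for week, three for treatment-by-week), with no new data. The SE rises by about 1% in the 50-woman scenarios (0.177 to about 0.179). With 40% of both months cut short at N = 40 it rises by about 3% (0.205 to 0.212). With complete data the estimate is unchanged. If the team prefers to keep the present primary model, the extended model could be run as a named sensitivity analysis.

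### For HFRDIS and DHFS, adjusting for imbalanced baseline variables as main effects says almost nothing about imbalance; adding their interaction with period would

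*Combined protocol and SAP*

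**What the plan says.** Section 12.1 analyses the repeated HFRDIS and DHFS values in a linear mixed model with "fixed effects for treatment, period, and treatment-by-period interaction, and random effects for subjects and for subject-by-treatment interactions". It fixes the estimand through the coding: "The period variable will be represented in the sum-to-zero coding so that the target of inference will be the fixed main effect of treatment".

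Two sensitivity analyses follow in one sentence: "the preliminary efficacy analyses will be repeated allowing for temporal correlation of measures", and a repeat "including as covariates any baseline variables with large imbalances". No interaction of those covariates with period or treatment is mentioned, and nothing says what agreement with the main analysis would be taken to show.

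Three other provisions matter here:
- Incomplete records stay in the model: "When observations of preliminary efficacy endpoints are missing, the rest of that patient's observations may still be used in the mixed effects model".
- The preliminary efficacy endpoints also include perceived efficacy, scored once per woman after her device month, with the two sequences compared.
- Allocation is unstratified (Section 4.3), and both groups give HFRDIS and DHFS scores on Day 0 (Section 7.2).

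**The concern.** In a parallel-group trial, adding an imbalanced baseline variable as a covariate is a sensible check, because the imbalance feeds directly into the treatment contrast. In a two-period crossover each woman is her own control, and her baseline level drops out before any adjustment.

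An imbalance between sequences can still distort the result if the variable predicts how scores change from the first month to the second. That is plausible here. Section 4.1.1 requires at least 28 hot flashes a week and a mean daily severity of at least 4/10, and women selected for high scores may decline in a way related to where they started. If one sequence has higher baseline scores by chance, part of that decline is counted as device effect or masks it. The planned check looks elsewhere. Section 2.0 makes effect sizes for a Phase III power calculation a secondary objective, so a distortion that goes unnoticed could carry forward.

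**Working it through.** The plan states no figure for this analysis, so there is none to reproduce. The effect of 0.7 (Cohen's d) in the Section 12.1 power statement serves only as a yardstick.

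**1. The target.** Let A be device first, B device second, and 1 and 2 the periods. In this design treatment-by-period is aliased with sequence, so the four cell means are saturated. With sum-to-zero period coding the treatment main effect is

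½[(A1 − A2) + (B2 − B1)].

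**2. Adding a baseline main effect.** With coefficient β and sequence means x̄A and x̄B, each cell mean is reduced by βx̄ of its own sequence. In A1 − A2 the term βx̄A appears twice with opposite signs and cancels; the same holds for B. With complete data the estimate is unchanged for any β and any imbalance.

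**3. Check by simulation.** The planned model was fitted by REML with and without the covariate. Assumptions not taken from the documents: within-subject SD 1, treatment-effect SD 1, residual between-subject SD 1.5, covariate slope 1, imbalance 0.8 SD. There were 4 values per period, as for weekly HFRDIS, and n was 38 or 50.

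| Data | Mean absolute change in treatment estimate | Largest change |
|---|---|---|
| Complete | 0 to rounding | 4e-15 |
| 15% scattered missing | 0.003 | 0.016 |
| 10–20% random dropout | 0.007–0.015 | 0.07 |
| 10–30% dropout related to the covariate | 0.02–0.05 | 0.18 |

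Standard errors with incomplete data were 0.18–0.24. The dropout rates are assumptions, since the plan gives none. With complete data the covariate acted on the interaction (sequence) term, which moved by about 0.8–1.0 and is not the target.

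**4. The bias that is missed.** Suppose the variable changes the shift from period 1 to period 2 by g per SD, and the sequences differ by D = x̄A − x̄B. With device effect τ and period effect π:

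- A1 − A2 = τ − π − g·x̄A
- B2 − B1 = τ + π + g·x̄B
- half the sum = τ − g·D/2

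The bias has size |g|·D/2, and the main effect of the covariate does not touch it. If the variable instead modifies the device effect by h per SD, half the sum is τ + h(x̄A + x̄B)/2, so a difference between sequences adds no bias.

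**5. Size.** Section 1.1 plans 25 women per sequence, so one standard error of a standardised baseline difference is √(2/25) = 0.28. The value of g is an assumption; two are shown.

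| D (SD) | g = -0.1 | g = -0.3 | g = -0.3, as share of 0.70 |
|---|---|---|---|
| 0.28 (1 SE) | 0.1 × 0.28 / 2 = 0.01 | 0.3 × 0.28 / 2 = 0.04 | 6% |
| 0.4 | 0.02 | 0.06 | 9% |
| 0.8 (about 2.8 SE) | 0.04 | 0.12 | 17% |

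**6. Does the alternative work?** In 15 simulated datasets of 50 women with a true effect of -0.70, g = -0.3 and D = 0.8, the mean estimate was -0.593 unadjusted, -0.593 with the planned covariate and -0.683 with covariate-by-period added. The Monte Carlo error is about 0.174/√15 = 0.045, so these means only illustrate the algebra in step 4.

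**The case against.** A reader might infer that the planned check can never change the result, so that agreement is guaranteed. The documents do not support this. Section 12.1 expects missing values and keeps partial records, which brings some between-woman information into the mixed model. In the incomplete-data simulations the estimate moved in every scenario, by up to 0.70 standard errors at worst, and significance at 5% changed in 0 to 3 of 60 datasets per scenario. The standard error can also shift by about 3% with complete data, depending on how the random effects are specified. This objection stands, though typical movements are small and come from missing data. They do not test whether the imbalanced variable predicts change between months.

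A reader might also infer that the phrase should simply be deleted. It should not. The same sentence covers perceived efficacy, a between-woman comparison in which imbalance can confound. With an assumed slope of 0.7 and an imbalance of 0.8 SD, adjustment there moved the difference by 0.56–0.57 on average, against standard errors of 0.34–0.39.

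Nor is change between months the only route by which imbalance could matter. Dropout related to an imbalanced variable is another. Section 12.1 addresses it separately, by comparing women who leave with those who stay and by multiple imputation.

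Finally, saying that the plan gives false reassurance goes too far, because it does not state how agreement would be read. The 17% figure should not be quoted alone: 0.8 SD is an extreme chance imbalance for a given variable at this sample size, and g is assumed.

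**Conclusion.** The point holds for the HFRDIS and DHFS mixed models. Main-effect adjustment leaves the treatment estimate exactly unchanged with complete data and usually nearly unchanged with partial records, so it is almost uninformative about baseline imbalance. The cancellation is algebra and needs no assumption beyond the stated model and complete data.

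The size of the missed bias depends on an assumed g. At g = -0.3 and a typical chance imbalance of one standard error it is about 0.04, roughly a quarter of the simulated standard error of 0.174 (0.04/0.174 = 0.23). It exceeds half a standard error only with a large imbalance (0.12/0.174 = 0.69 at 0.8 SD).

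Severity is minor. No primary result or decision rule rests on this analysis, and the reason to act is that a better check costs one sentence.

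**What to change.** In Section 12.1, split the covariate sensitivity analysis by endpoint:

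- **HFRDIS and DHFS mixed models:** include any largely imbalanced baseline variable, centred, together with its interaction with period. This covers the baseline score of the outcome itself, if that is imbalanced.
- **Perceived efficacy:** keep main-effect adjustment. Each woman has one score, taken at the end of her device month, so a period interaction there would only be an interaction with sequence.

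Centring keeps the period effect readable. It does not alter the treatment estimate, because shifting x by a constant c changes period × x only by c × period, which the period term absorbs.

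No new data are needed for the baseline scores, since both are collected on Day 0. The cost is a somewhat wider interval in this sensitivity analysis only. In simulation the standard error rose from 0.174 to 0.186 with one covariate at 0.8 SD imbalance (0.186/0.174 = 1.07). The cost grows with the number of interactions, which is a reason to limit them to variables with large imbalances in a trial of 50 women.
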